13.2 Other committees

Membership of the TSC (which will incorporate IDMEC), has been agreed and can be seen below.

TSC Members

[name] (Chair), Honorary Professor, Division of Psychiatry, Faculty of Brain Sciences, UCL, Independent Member

[name], Family Carer, Uniting Carers for dementia (UKfd), Independent Member

[name], Member of the Public, Public governor of the Black Country Partnership NHS Foundation Trust and Shadow Public Governor of the Dudley and Walsall Mental Health Trust, Independent Member

[name], (PI)

[name], (CI)

[name], Trial Statistician

The role of the TSC is to provide overall supervision of the trial, recommendations in relation to data monitoring, and, on consideration of this information, recommend any appropriate amendments/actions for the trial as necessary. Note that given that this is feasibility trial the TSC is also acting as an IDMEC. The TSC will also act on behalf of the funder and Sponsor, and will provide independent advice on data and safety aspects of the trial. Meetings of the Committee will be held twice a year to review progress and address any issues as necessary. Since the TSC is acting as the IDMC, it can recommend premature closure of the trial.

14 Ethical requirements and patient and public involvement

Ethics

The sponsor will ensure that the trial protocol, PIS forms, ICFs, GP letter and submitted supporting documents have been approved by the appropriate Research Ethics Committee (REC), prior to any participant recruitment. The protocol, all other supporting documents including and agreed

amendments, will be documented and submitted for ethical and regulatory approval in line with Governance Arrangements for NHS Research Ethics (GAfREC) and Quality Assurance (QA) guidelines. The study will be approved by the appropriate local governance procedures such as National Health Service Research & Development (NHS R&D). Ethical concerns arising from the study will be reviewed by the TSC and IDMEC. All researchers will receive training in line with the GCP guidelines. The study has been registered as a clinical trial and has been allocated an International Standard Randomised Controlled Trial Number ISRCTN number ID (ISRCTN75503960). As the intervention is psychological the trial is not covered by the Medicines for Human Use (Clinical Trials) Regulations 2004.

Amendments will not be implemented prior to receipt of the required approvals. Before any NHS site may be opened to recruit participants, the PI/CI or designee must receive NHS permission in writing from the Trust Research & Development (R&D). It is the responsibility of the PI/CI or designee at each site to ensure that all subsequent amendments gain the necessary approvals, including NHS Permission (where required) at the site. This does not affect the individual clinician's responsibility to take immediate action if thought necessary to protect the health and interest of individual participants (see section 9.6 for reporting urgent safety measures). An annual progress report (APR) will be submitted to the REC within 30 days of the anniversary date on which the favourable opinion was given, and annually until the trial is declared ended. The PI will prepare the APR. Within 90 days after the end of the trial, the PI/Sponsor will ensure that the main REC is notified that the trial has finished. If the trial is terminated prematurely, those reports will be made within 15 days after the end of the trial.

The PI will supply the Sponsor with a summary report of the trial, which will then be submitted to the REC within 1 year after the end of the trial.

Patient and public involvement (PPI)

We have consulted local user groups of carers and people with dementia, and professionals supporting them to ensure the project is likely to be meaningful for people with dementia. We conducted an initial consultation via the local Mental Health NIHR Clinical Research Network (DeNDRoN, mental health, neurological disorders). Feedback from this consultation suggested that this will be an important intervention to offer to people with dementia, and their families. We have received further feedback about this project from people with dementia via The Camden Minds Support group which forms part of the Dementia Engagement & Empowerment Project (DEEP), bringing together groups of people with dementia across the UK, consulting researchers and advocating for changes in policies affecting the lives of people with dementia. People with dementia commented that they thought the intervention will be a useful one, providing opportunities to 'talk about feeling low' and finding ways to feel better. Further comments have been received by lay volunteers from the Alzheimer's Society. These emphasised the importance of incorporating social elements to the intervention as this will help keep depression 'at bay', and incorporating pleasant activities (this will be a key component of the intervention).

We will develop a dissemination strategy that will identify the groups who will need to be communicated of the results and the methods we will use in order to disseminate the study's findings. The strategy will be developed at an early stage in consultation with the Patient and Public Involvement (PPI) group members. We will consult our PPI representatives in relation to audience for

dissemination, and the communication channels that will be used. We will develop and disseminate regular newsletters informing clinicians and mental health professionals in the relevant Trusts of the progress of the study. We will disseminate the study findings in peer-reviewed publication journals. Study findings will also be presented at research conferences, and local symposiums. We will also inform GPs and other key dementia care professional groups.

The *Patient and public involvement* group for the project comprises of the following members:

[name], PPI member. [name] is the Dementia Befriending Project Coordinator, for Age UK Camden. She has worked in support services for people with dementia and their families for many years.

[name], PPI member. [name] is an ex carer and an Alzheimer's network volunteer for over 10 years. She also has advised and provided expertise on patient and public involvement in many projects for NIHR.

15 Monitoring

The sponsor will determine the appropriate level and nature of monitoring required for the trial. Standard Operating Procedures (SOPs) of the Sponsor will be followed. Risk will be assessed on an ongoing basis and adjustments will be made accordingly. The degree of monitoring will be proportionate to the risks associated with the trial. A trial specific oversight and monitoring plan has been established. The trial will be monitored in accordance with the agreed plan. We will follow GCP by monitoring participants for suicide risk throughout the duration of the trial and in all contacts with participants. If any risk of self-harm or harm to others is detected the PI will contact the NHS Clinical Team and the person who referred the participant. We will monitor data of the Cornell Scale for Depression in Dementia (CSDD) which allows us to screen for suicidal ideation via the question: "During the past week, has your relative had any thoughts that life is not worth living or that s/he would be better off dead? Has s/he had any thoughts of hurting or even killing him/herself? Incidents will be recorded and reported to the IDMEC, TSC, sponsor of the trial and ethics committee and if serious or life threatening will be reported within 15 days of knowledge.

16 Finance

This project is funded by the Alzheimer's Society, as part of a Senior Fellowship Award to the PI. This fellowship award covers the salary of the PI. There are no financial interests for the PI, CIs or programme management or TSC members.

17 Insurance

University College London holds insurance against claims from participants for injury caused by their participation in the trial. Participants may be able to claim compensation if they can prove that UCL has been negligent. However, as this trial is being carried out in a hospital, the hospital continues to

have a duty of care to the participant of the trial. University College London does not accept liability for any breach in the hospital's duty of care, or any negligence on the part of hospital employees. This applies whether the hospital is an NHS Trust or otherwise.

Participants may also be able to claim compensation for injury caused by participation in this trial without the need to prove negligence on the part of University College London or another party. Participants who sustain injury and wish to make a claim for compensation should do so in writing in the first instance to the PI, who will pass the claim to the Sponsor's Insurers, via the Sponsor's office.

Hospitals selected to participate in this trial shall provide negligence insurance cover for harm caused by their employees and a copy of the relevant insurance policy or summary shall be provided to University College London, upon request.

18 Publication policy

A publication dissemination policy will be developed as part of this project. Publications arising directly or indirectly from the IDEA project will adhere to the UCL and BMJ (2009) guidelines on authorship and contributorship. These state that 'authorship credit should reflect substantial contribution to:

- conception and design, or analysis and interpretation of data;
- drafting the article or revising it critically for important intellectual content;
- and final approval of the version to be published.

All these conditions must be met. All proposed publications will be discussed with and reviewed by the Sponsor prior to publishing other than those presented at scientific forums/meetings.

19 Intellectual property

All background intellectual property rights (including licences) and know-how used in connection with the study shall remain the property of the party introducing the same and the exercise of such rights for purposes of the study shall not infringe any third party's rights.

All intellectual property rights and know-how in the protocol and in the results arising directly from the study, but excluding all improvements thereto or clinical procedures developed or used by each participating site, shall belong to UCLH. Each participating site agrees that by giving approval to conduct the study at its respective site, it is also agreeing to effectively assign all such intellectual property rights ("IPR") to UCL and to disclose all such know-how to UCL. Each participating site agrees to, at the request and expense of UCL execute all such documents and do all acts necessary to fully vest the IPR in UCL.

Nothing in this section (Section 19) shall be construed so as to prevent or hinder the participating site from using know-how gained during the performance of the study in the furtherance of its normal activities of providing or commissioning clinical services, teaching and research to the extent that such use does not result in the disclosure or misuse of confidential information or the infringement of an intellectual property right of UCL. This does not permit the disclosure of any of the results of the study, all of which remain confidential.

20 Appendices

Enrolment
Memory Clinics and Community Mental Health
Teams in 2 London NHS Trusts

[figure not shown]

Figure 1. Flow diagram of recruitment and follow-up of participants in the feasibility RCT and outcomes assessed for suitability for the full trial.

Appendix 1 - Flow diagram of recruitment and follow-up of participants

IDEA Project timetable and milestones

February 2016	Start of the IDEA Project
February 2016 – July 2016	Ethics Approval
May 2016 – October 2016	Appointment of Research Assistant
February 2016 – September 2016	Systematic review of Behavioural Activation interventions for older people – Work Package 1
August 2016 – October 2016	First draft of the IDEA Intervention Manual – Work Package 1
November 2016 – January 2018	Recruitment for Work Package 2 & 3
November 2016 - February 2017	Consultations with users, carers and dementia care professionals about the IDEA Intervention Manual – Work Package 2
February 2017	Consultation with Experts/ Experts Workshop about the IDEA Intervention Manual - Work Package 2
March 2017	Analyses of Qualitative data - Work Package 2
March 2017	Second draft of the IDEA Intervention Manual - Work Package 2
February 2017 – April 2017	Development of all Intervention Materials
April 2017 – May 2017	Field-testing of the Intervention
May 2017 – July 2017	Intervention Refinement – Final draft of the IDEA Intervention Manual
August 2017 – January 2017	Feasibility RCT
October 2017 – March 2018	Follow-up assessments at 4 months
February 2018 – July 2018	Follow-up assessments at 8 months
July 2018 – October 2018	Analyses of feasibility data
May 2018- October 2018	Publication of qualitative findings
February 2019 – July 2019	Publication of feasibility RCT findings
November 2019	Dissemination event
August 2019- January 2020	Grant Application for main Trial

Appendix 3 - References

	Screening (Pre-treatment assessment)	Intervention phase								1 st Follow-up Visit	2 nd Follow-up Final visit
Visit No:	1	2	3	4	5	6	7	8	9	10	11
	Day 1	Day 1	Day 2	Day 3	Day 4	Day 5	Day 6	Day 7	Day 8	Day 1	Day 1
Window of flexibility for timing of visits:	N/A	e.g. +/- 2 weeks	e.g. +/- 2 weeks	e.g. +/- 2 weeks	e.g. +/- 2 weeks	e.g. +/- 2 weeks	e.g. +/- 2 weeks	e.g. +/- 2 weeks	e.g. +/- 2 weeks	e.g. +/- 4 weeks	e.g. +/- 4 weeks
Informed Consent	X										
Eligibility confirmation	X										
Protocol Assessments	Cornell Scale for Depression in Dementia									Cornell Scale for Depression in Dementia	Cornell Scale for Depression in Dementia
	DEMQOL (Quality of Life)									DEMQOL (Quality of Life)	DEMQOL (Quality of Life)
	Neuropsychiatric Inventory									Neuropsychiatric Inventory	Neuropsychiatric Inventory
	Client Service Receipt Inventory									Client Service Receipt Inventory	Client Service Receipt Inventory
	Hospital and Anxiety Depression Scale (Carer anxiety and depression)									Hospital and Anxiety Depression Scale (Carer anxiety and depression)	Hospital and Anxiety Depression Scale (Carer anxiety and depression)

	EuroQoL EQ-5D (Carer Quality of life)										EuroQoL EQ-5D (Carer Quality of life)	EuroQoL EQ-5D (Carer Quality of life)
	Short Form questionnaire-12 (Carer mental health)										Short Form questionnaire-12 (Carer mental health)	Short Form questionnaire-12 (Carer mental health)
Intervention Assessment		Behavioural activation session with graduate psychologist	Behavioural activation session with graduate psychologist	Behavioural activation session with graduate psychologist	Behavioural activation session with graduate psychologist	Behavioural activation session with graduate psychologist	Behavioural activation session with graduate psychologist	Behavioural activation session with graduate psychologist	Behavioural activation session with graduate psychologist	Behavioural activation session with graduate psychologist		
Intervention Assessment									Behavioural activation Qualitative Interview			
Randomisation	X											
Adverse Events review	X	X			X				X	X	X	X

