Generally we do not anticipate any risks to people with dementia through participation. The information sheets will provide participants with information about the possible benefits and known risks of taking part in the trial. Participants will be given the opportunity to discuss this with the researcher prior to consenting to the study. There appear to be no documented harmful side effects from taking part in behavioural activation interventions. The only potential risk we can identify associated with the proposed research is that people may find either the intervention or the assessments upsetting or distressing, for example highlighting pleasant activities that they can no longer do, or do so independently. However given previous preventive trials of behavioural activations in several populations, and the Cochrane review published by the PI on psychological interventions for people with dementia, this is expected to be infrequent. Most people find behavioural activation sessions enjoyable, and feel comfortable in taking part in these types of interventions. At any point where a participant or carer becomes uncomfortable with the assessments they will be discontinued. The researcher running the sessions and completing the assessments will be advised to discontinue the assessment/intervention sessions, and participants will be given further support and will be debriefed as necessary. For example, they will be encouraged to **Speak to one of the team members, and/or ring the Alzheimer's Society National Dementia Helpline (see Participant Information Sheets)**. Local lone working policies for all staff involved will apply in relation to assessment and management of risk for UCL staff.

4 Objectives

Primary: The primary objective of the study is to develop a coping intervention based on behavioural activation to prevent depressive symptoms arising or worsening and promote well-being in people with early-stage dementia.

Secondary: The secondary objective is to assess the feasibility and acceptability of the intervention via a feasibility RCT in order to inform a future fully powered RCT of clinical and cost-effectiveness.

5 Trial design

Study design: Feasibility RCT, of 2 treatment arms (Behavioural Activation vs treatment as usual) over 8 weeks, assessing the acceptability and feasibility of behavioural activation for preventing depressive symptoms in early-stage dementia (see Figure 1, in Appendix 1).

6 Selection of Participants

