8.1 Pre-intervention assessments

There are no specific pre-intervention assessments other than screening participants for inclusion criteria and the baseline assessments. People with dementia that meet the inclusion criteria and their carers will be recruited from several settings and existing networks (i.e. Community Mental Health Teams for Older People (CMHTs), Memory Clinics, Outpatient Clinics, Day centres). Baseline information required for eligibility will be recorded by memory clinics, day centres, and CMHTs. Participants will be recruited by engaging with professionals in the above settings and will be identified by the researcher using the networks above. We will use RCT methodology with remote randomisation, which will be provided by Sealed Envelope. There is a Master Services Agreement between UCL and Sealed Envelope in place. The PI will complete a trial registration form to be completed with all the details for the study and then signed off by a UCL Research Contract Manager, at University College London. See Section 8.4 for details of assessment procedures.

All pre-treatment procedures will be carried out as specified in the schedule of assessments (Appendix 4).

Treatment as usual

This study is designed to be a pragmatic trial, and no participants will be denied access to any treatment that they would have access to have they not taken part in the study. Both groups will also receive care as usual, details of which will be recorded for each participant. The treatment as usual control group (TAU) will not receive any additional intervention. We will assess the feasibility of collecting service use data, which will allow us to identify services received in both groups and any changes that occur.

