8.3 Intervention procedures

The proposed intervention will aim to:

- (1) increase the use of effective coping strategies for people with early-stage dementia by:
 - (a) identifying pleasant activities and agreeing to a plan of which activities to implement
 - (b) setting goals about implementing these
 - (c) monitoring and reviewing activities (on a weekly basis)
 - (d) teaching specific simple skills coping with stress (51)
 - (e) discussing accessing help
- (c) make a plan for the future

The intervention will be an individual home-based manualised programme, comprised of a total of 8 sessions. Participants and carers can repeat a session or a part of a session when necessary, and each of the sessions will last approximately 45 minutes (with homework between the sessions). The intervention will be delivered by a psychology graduate who will be trained in the intervention by the team. The psychology graduate will be supervised monthly by one of the CIs who is a Clinical Psychologist ([name]).

Adherence to treatment protocol

We will develop a manual guiding therapists in delivering the intervention. This manual will describe the key components of the intervention and will also specify training elements. We will also test the feasibility of measures assessing treatment adherence, such as audiotaping some of the sessions, and competency assessment, by developing a checklist for use in the main trial. This checklist will assess whether behavioural activation was the overall modality applied and if other therapeutic models were prominent in the therapy (i.e. cognitive therapy).

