8.4 Subsequent assessments and procedures

This section describes all proposed outcome measures and assessments at each home visit.

Proposed outcome measures

Feasibility outcome measures

- The acceptability of the intervention for people with dementia and their carers (number of those finding the intervention acceptable)
- Willingness of clinicians to recruit and people with dementia to be randomised (number of dyads recruited per month and any barriers or facilitators to recruitment)
- Number of eligible participants that consent to the study
- Follow-up rates and number completing each outcome measure proposed for the main trial
- Number of sessions attended
- Standard deviations of outcome measures to estimate the sample size in a fully powered RCT

The acceptability of the programme to people with dementia, willingness of clinicians to recruit participants and of participants to be randomised, will be collected for feasibility analysis. We will also collect data on recruitment, attrition and questionnaire completion rates and estimate 'numbers needed' to plan a fully powered RCT of clinical and cost-effectiveness. Feasibility data on acceptability, completion rates and attrition will be supplemented by qualitative data. During qualitative interviews information will be collected on which outcomes will be of value to people with dementia, data relevant to the trial process itself, the randomisation procedure, and the methods of data collection.

Proposed clinical outcome measures

These will be evaluated for suitability for the main trial. Depressive symptoms is proposed as the outcome for the future fully powered study. Carers will complete generic health and quality of life measures (EQ-5D, SF-12), and resource use questionnaires to examine feasibility of cost-effectiveness analysis. Questionnaires will be completed at baseline, 4 and 8-months after randomisation.

Primary outcomes

1. depressive symptoms - *Cornell Scale for Depression in Dementia (CSDD)* (58). The CSDD, is a 19-item interviewer administered measure, using information by interviewing the person with dementia and their carer. Symptoms are described to the carer as they appear on the scale. Where there is a discrepancy between the carer and the researcher's ratings the carer is re-interviewed before making a final judgment.

Secondary outcomes

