9.1 Unblinding

Protection against bias

In trials of psychological interventions, therapists and participants can not be blind to which intervention they are delivering or receiving. However assessors conducting assessments with participants, should not be aware of which treatment arm they belong to. All follow-up assessments after the intervention will be conducted by a researcher who is blind to treatment allocation. Given that participants may occasionally and inadvertently inform researchers of the treatment they are receiving, we will reduce this effect by providing explicit reminders to participants. We will record instances of loss of blinding to inform procedures for the main trial.

Emergency unblinding:

This section is Not Applicable to this project as it is a single-blinded trial. We will seek advice on issues of blinding by the UCL Research Service and Senior Trialists in the Division of Psychiatry.

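### Adverse-event reviews are tied partly to sessions that, on the natural reading, only the behavioural activation arm attends, so recorded counts by arm are not like for like

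*Protocol*

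**What the plan says.** Appendix 4 is a single grid of 11 visits with no separate version for TAU. Its row "Adverse Events review" is marked at visit 1, at about visits 2, 5 and 9, and at the two follow-up visits. The extracted row has one more cell and one more mark than 11 visits can hold, so the number of intervention-phase reviews is three or possibly four. That is a fault of extraction, not of the plan.

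Each of visits 2 to 9 is labelled "Behavioural activation session with graduate psychologist". Section 8.3 agrees: "The intervention will be an individual home-based manualised programme, comprised of a total of 8 sessions".

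For the control arm, Section 8.1 says: "The treatment as usual control group (TAU) will not receive any additional intervention". The contacts described for both arms are those in Section 8.4: "Questionnaires will be completed at baseline, 4 and 8-months after randomisation".

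Section 9 is headed as covering adverse events, but its subsections deal with blinding, protocol violations and Trust incidents. None says how events are collected in TAU. Section 13.2 gives the safety role to the TSC: "Since the TSC is acting as the IDMC, it can recommend premature closure of the trial".

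**The concern.** How many events are recorded depends on how often, how soon and by whom people are asked. On this schedule a BA participant is asked several times during the sessions. A TAU participant is first asked at the 4-month visit, or at about five months if the 4-week window is fully used. The informants are people with dementia and their carers, so recall over that interval matters.

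The person asking also differs. The session reviews fall at visits with the therapist, who knows the allocation, whereas Section 9.1 says: "All follow-up assessments after the intervention will be conducted by a researcher who is blind to treatment allocation".

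Other safety routes follow contact as well. Under Section 15, suicide risk is monitored at contacts with participants. Under Section 9.3, Trust incidents are reported once staff become aware of them. Neither makes up for the missing TAU contacts.

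At stake is what the TSC sees when it gives advice on safety. An arm-level count built on this schedule mixes any real difference with a difference in asking.

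**Working it through.** The protocol states no adverse-event rate or ratio, so there is no figure to reproduce. The check is a count, followed by an illustration on assumed values.

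**1. Scheduled reviews (Appendix 4; TAU column inferred)**

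| Period | BA | TAU |
|---|---|---|
| After randomisation, before the 4-month visit | 3 (visits 2, 5, 9); 4 if the surplus mark is real | 0 |
| 4- and 8-month visits | 2 | 2 |
| Total after randomisation | 5 (or 6) | 2 |

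No reading of the broken row shows a TAU review during the session phase.

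**2. Illustration with fixed capture rates**

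Inputs from the protocol: the intervention phase, from Section 5, "Feasibility RCT, of 2 treatment arms (Behavioural Activation vs treatment as usual) over 8 weeks"; and follow-up at 4 and 8 months, that is 4 × 52/12 = 17.3 weeks and 34.7 weeks.

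Assumed inputs: equal true event rates; 80% of events captured when asked about within weeks; a proportion *c* of 65% or 50% captured at the later visit. Once the sessions end, both arms are next asked at the same visits, so capture is *c* in both.

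BA:TAU ratio of recorded events over *T* weeks:

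R = [8 × 0.80 + (T − 8) × c] / (T × c) = 1 + (8/T) × (0.80/c − 1)

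| c | T = 17.3 weeks | T = 34.7 weeks |
|---|---|---|
| 0.65 | 1 + 0.462 × 0.231 = 1.11 | 1 + 0.231 × 0.231 = 1.05 |
| 0.50 | 1 + 0.462 × 0.600 = 1.28 | 1 + 0.231 × 0.600 = 1.14 |

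**3. Sensitivity to the form of recall**

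A second assumed model records an event at the next review with probability exp(−lag/τ). Assumed BA reviews are at weeks 1, 4 and 8 and months 4 and 8; TAU reviews are at months 4 and 8. The captured share is the sum over review intervals *L* of τ(1 − exp(−L/τ)), divided by *T*.

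| τ (weeks) | Ratio, 0–4 months | Ratio, 0–8 months |
|---|---|---|
| 4 | 2.31 | 1.66 |
| 8 | 1.71 | 1.35 |
| 12 | 1.47 | 1.24 |
| 26 | 1.21 | 1.11 |
| 52 | 1.11 | 1.05 |
| perfect recall | 1.00 | 1.00 |

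This model gives larger ratios when recall fades quickly, because the TAU events that go unasked longest are exactly those from the session weeks. In neither model does the ratio fall below 1 at equal true rates.

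**4. Could chance hide it?**

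Take the upper four-month value from step 2 and treat counts as Poisson with equal person-time (an assumption; the allocation ratio is not stated). With *b* events in TAU and 1.28*b* in BA, the variance of the log ratio is (1/b)(1 + 1/1.28) = 1.78/b. Setting ln 1.28 = 0.247 equal to 1.96 standard errors gives b = 1.78 × (1.96/0.247)² ≈ 112 events in TAU, so about 2.28 × 112 ≈ 255 in total. That is more than four per dyad in 60 dyads over four months. With fewer events, chance variation can easily hide or exaggerate the effect.

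**The case against.** **No by-arm comparison of adverse events is planned.** They are in neither outcome list, and analyses are descriptive. Section 11.6.4 defers detail to a separate analysis plan, which may settle the tables. This stands, and it makes the point conditional on someone tabulating or reviewing events by arm. It does not dispose of it: the review schedule and the question asked are fixed before data collection, and a later plan cannot recover events forgotten before anyone asked.

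**Other common sources exist.** The service-use inventory, the Cornell scale with its suicidal-ideation question and the Neuropsychiatric Inventory are given to both arms at the same visits. They cover events that lead to service use, suicidal ideation and behavioural disturbance. They do not equalise capture of lesser events.

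**The TAU side is inferred.** Section 8.1 rules out additional intervention, not contact. That is fair, but no TAU contact before four months is described anywhere.

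**Extra review at sessions is defensible.** The section on assessment and management of risk names distress from the intervention or the assessments as the one potential risk, and unequal contact is inherent in a usual-care control. Agreed; the difficulty is only in pooling those reviews into a comparison.

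**Stronger readings that the protocol does not support.** A reader might infer that BA will look less safe. That is only the expected direction at equal true rates. A reader might divide the assumed capture rates directly (0.80/0.65 = 1.23; 0.80/0.50 = 1.6) and apply the result to the whole four months. The sessions last 8 weeks, and after them both arms wait for the same visit. A reader might infer that biased event rates will enter main-trial planning, but event rates are not among the listed inputs. Finally, the TSC may recommend closure, but no event threshold or stopping rule based on an arm-level count is stated.

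**Conclusion.** The point holds in conditional form. The schedule gives about 5 post-randomisation reviews in BA against 2 in TAU, and 3 against 0 before the 4-month visit. If events are tabulated or reviewed by arm, more recorded events are expected in BA at equal true rates.

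On the fixed capture rates assumed above, the excess is a ratio of about 1.1–1.3 over the first four months and 1.05–1.14 over eight. These are illustrations. The protocol gives no capture rate and defines no recall period; faster fading of recall would raise the ratio and perfect recall would remove it. The conclusion also rests on reading visits 2 to 9 as BA-only. The change is worth making because it is cheap and must be in place before data are collected.

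**What to change.** - At the 4- and 8-month visits, ask one identical structured adverse-event question with the same recall period in both arms, whatever was noted at sessions.
- State that any by-arm summary, including reports to the TSC acting as data monitoring committee, uses only those shared visits.
- List events noted at BA sessions in a separate BA-only table.
- Leave safety monitoring at sessions and incident reporting unchanged.
- State in Appendix 4 which visits apply to TAU.

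The cost is some protocol and analysis-plan wording and one case report form question; no visits are added. There are two drawbacks. BA participants asked again about events they have already described may reveal their allocation to the blinded assessor. The reminders to participants and the record of lost blinding in Section 9.1 should cover this question. Earlier questioning may also help BA participants remember, so shared-visit counts will be closer to comparable but not fully so, and the report should say this.
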